Specific Aim: To determine whether hydroxychloroquine use during pregnancy prevents the recurrence of CHB.

This will be approached in an open label Phase II trial entitled: Preventative Approach to Therapy for Congenital Heart Block with Hydroxychloroquine (PATCH), in pregnant women who have had a previous child with CHB. This is designed as an open-label trial employing Simon's 2-stage optimal

design to allow for early stopping due to absence of treatment efficacy. The first stage requires 19 subjects, which are expected to be enrolled in the year of this award. Despite the rarity of disease and the requirement of a previous child with CHB, based on the US Research Registry for Neonatal Lupus (RRNL) and data from the UK, this proposal is feasible. If 3 mothers have a child with 2nd or 3rd degree CHB, the study is terminated after the first stage. Serial echocardiograms (monitor PR interval) and evaluation of biomarkers (HCQ levels, IFN*a* signatures, and Ab titers) will be part of the protocol. The results of this study should become an integral component of the counseling of women with anti-Ro/La Ab who are considering pregnancy.

Background

CHB associated with maternal anti-Ro Ab has a high mortality (20-30%, primarily fetal/neonatal) and morbidity (67% require permanent pacing before adulthood) [6,7]. In addition to conduction disease, 10-15% of affected offspring will have a life-threatening cardiomyopathy [8,9]. Histopathologic studies constitute a major basis for formulating hypotheses regarding the pathogenesis of CHB, which in turn guide the rationale for therapeutic approaches. Studies of several fetal hearts identified in utero with CHB or isolated myocarditis revealed that fibrosis is extensive and replaces the AV node, even in 20 and 22 week hearts [10], supporting the clinical observation that 3rd degree CHB is irreversible. The identification of a macrophage infiltration in fetuses dying most proximate to the time of diagnosis suggests that inflammation may be integral to the development of fibrosis [10].

Prenatal Considerations

From an immunologic perspective, reduction of a generalized inflammatory response has traditionally been considered a logical approach to the prevention or treatment of CHB. The use of maternal oral dexamethasone has been popularized by several groups but its scientific merit is underwhelming, and the risks may be substantial [11-13]. The PRIDE (PR Interval Dexamethasone Evaluation) in CHB study revealed no reversibility of 3rd degree CHB with dexamethasone, a higher mortality with dexamethasone (albeit these may have been sicker fetuses), and inconsistent effects on reversal of incomplete blocks [14].

Intravenous Immunoglobulin G (IVIG): A prospective study in which feasibility of recruitment and reproducibility of the recurrence rate was demonstrated but prevention of CHB was not achieved:

The consideration of IVIG in the prevention of CHB was based on our working hypothesis of the pathogenesis of disease. Tissue injury in the fetus is presumed to depend on the Fc Rn-mediated transplacental passage of maternal IgG Ab [15]. Anti-Ro/La Ab, by binding to translocated antigens on the surface of apoptotic cardiocytes generated during remodeling of the conduction system and surrounding tissue, may inhibit the normal physiologic removal of these cells [16]. Uncleared opsonized apoptotic cardiocytes may be subsequently efferocytosed by infiltrating macrophages with release of pro-inflammatory and profibrosing cytokines which transdifferentiate cardiac fibroblasts to a scarring phenotype [17]. This scenario supported the consideration of prophylactic therapy with IVIG based on 2 presumed mechanisms of efficacy. The first relates to the saturation of Fc Rn by IVIG, which would be expected to decrease fetal exposure to anti-Ro/La Ab by accelerating IgG catabolism in the maternal circulation and by decreasing placental transport [18]. The second relates to the potential attenuation of anti-inflammatory responses by increasing the macrophage expression of Fc RIIB [19]. This would represent a downstream effect in the targeted organ.

Accordingly, a multicenter, prospective, open-label study in the U.S. was initiated [2] (Preventative IVIG Therapy for CHB, PITCH). Enrollment criteria included the presence of anti-Ro Ab in the mother, birth of a previous child with CHB/neonatal lupus rash, current treatment with 20 mg/day of prednisone, and <12 weeks pregnant. IVIG (400 mg/kg) was given every 3 weeks from gestational week 12 - 24. The primary outcome was the development of 2nd or 3rd degree CHB. Twenty mothers completed the IVIG protocol before the predetermined stopping rule of 3 cases of advanced CHB was reached. CHB was detected at 19, 20, and 25 weeks; none occurred following a prolonged PR interval. One of these 3 mothers had 2 previous children with CHB. One child without CHB developed a transient rash consistent

with neonatal lupus. Sixteen children had no manifestations of neonatal lupus at birth. No significant changes in maternal titers of Ab to Ro60, Ro52, or La48 were detected over the course of therapy or at delivery. There were no safety issues.

In parallel with enrollment of the PITCH study, a European study was initiated in December, 2004. We and the P.I., [name], had agreed on the protocol. The study was terminated after 3 recurrent cases of CHB were identified following enrollment of 15 mothers [3]. Combining data generated from the U.S. and the European PITCH studies, there were 6 (18%) recurrences in 33 women who had previous pregnancies complicated by CHB. Each study was originally designed to conclude inefficacy of IVIG if 6 cases of 54 were identified. However, since the chances of one further recurrence in the next 21 (if combined US and UK) was greater than 98% assuming the 18% recurrence rate observed, the trial was deemed futile and terminated.

Hydroxychloroquine: A potential prophylactic approach

Antimalarials are among the most frequently prescribed medications in SLE patients. The prevention of flares and reduction of mortality are associated with the use of these medications as supported by a recent systematic review of high quality published evidence [20]. Serious adverse events such as cardiotoxicity are rare, even after prolonged use. With regard to retinal toxicity, CQ appears to be more toxic than HCQ [20].

The use of antimalarials to prevent SLE flares during pregnancy has been addressed by several In a small, randomized double-blind trial of 10 SLE pregnant patients receiving HCQ studies. (surprisingly, dose not stated) compared to 10 on placebo, the drug was administered between 8 - 18 weeks of gestation [21]. In the active drug group, there were no flares of disease activity compared to 3/10 in the placebo group. Importantly, neither congenital abnormalities at birth nor ophthalmologic or auditory abnormalities were detected up to a minimum follow up of 1.5 years. A second study, nonrandomized, compared three groups of pregnant patients: those continuously exposed to HCQ before and throughout pregnancy (N = 56), those with no exposure (N = 163), and those in whom HCQ was discontinued prior to or during the first trimester (N = 38) [22]. The patients who discontinued HCQ were reported to have a higher degree of SLE activity and an increased frequency of flares. Ophthalmologic and auditory tests were limited to routine infant care although the authors did not report any clinically significant fetal abnormalities attributable to HCQ exposure. A third study showed that discontinuation of HCQ at the onset of pregnancy was associated with increased lupus activity [23]. Our own data from the Prospective Predictors of pRegnancy Outcome: bioMarkers In Antiphospholipid Antibody Syndrome and Systemic Lupus Erythematosus (PROMISSE) study also suggested the benefit of HCQ. Specifically, 105 patients with SLE were taking HCQ throughout pregnancy [24]. Overall, mild/moderate and severe flares were infrequent (<10%) and maintaining HCQ during pregnancy appeared to be of benefit in preventing flares. One child was reported to have an abnormal audiology screen at birth, which was considered inconsequential upon subsequent testing.

Despite accumulating evidence supporting the prevention of SLE flares during pregnancy, some physicians may remain reluctant to prescribe HCQ given isolated case reports of auditory toxicity [25] and retinal toxicity [26] in fetuses exposed to HCQ, in addition to data from an animal model regarding retinal deposition [27]. Currently, the FDA lists both CQ and HCQ as pregnancy risk category C (safety in human pregnancy has not been determined). However, recent reviews of the literature suggest that, in particular, HCQ is safe to use during pregnancy [20,28,29]. None of the studies (inclusive of over 250 children) found an increased frequency of congenital malformation. In 58 children tested, maternal use of HCQ was not associated with either hearing or visual abnormalities [28]. Available ECGs revealed no differences with regard to duration of the PR or QTC intervals between unexposed or exposed children [28].

The rationale for HCQ rests on translation of the pathophysiology of CHB which likely involves a complex cascade linking antibody to ultimate scar. Dual receptor signaling via uptake of the anti-Ro/La immune complexes by $Fc\gamma R$ on macrophages, and delivery of associated ssRNA to the endosomal compartment for ligation with Toll Like Receptors (TLR7/8) may be critical steps toward

conduction damage. Since endosomal TLR binds ligand at low pH, pharmacologic approaches to attenuate TLR-dependent readouts have utilized CQ and bafilomyocin which interfere with acidification [30,31]. Our own laboratory has recently demonstrated that both macrophage transfection with non-coding ssRNA that bind Ro60 and an immune complex generated by incubation of Ro60-ssRNA with an IgG fraction from a CHB mother or affinity purified anti-Ro60 significantly increased TNF secretion, an effect not observed using control RNAs or normal IgG. Dependence on TLR was supported by the significant inhibition of TNF release by IRS661 (inhibits TLR7) and CQ. Fibrosis markers were noticeably increased in fetal cardiac fibroblasts after incubation with supernatants generated from macrophages transfected with ssRNA or incubated with the immune complex, an effect abrogated by IRS661 or CQ [4]. These in vitro findings generate the hypothesis that HCQ, which reduces the acidification required for optimal ligation of TLR and has been shown to be safe in pregnancies, as detailed above, may prevent cardiac tissue injury associated with antibodies to these ssRNA-complexed proteins.

Another potential mechanism favoring efficacy in preventing CHB, is that HCQ by virtue of reducing endosomal acidification might also decrease transplacental transport of maternal antibodies. This possibility is supported by the fact that maternal IgG is pinocytosed at the apical surface of the syncytiotrophoblast into an acid endosomal compartment containing FcRn, and migrates via transport vesicles to the basolateral surface of the cell, where at physiologic pH it uncouples from the receptor (15).

Study Design

Nineteen women in Stage 1 and an additional 51 women in Stage 2 (if reached, for a total of 70 subjects) meeting eligibility criteria will receive 400mg per day of HCQ beginning as soon as pregnancy is established and informed consent obtained. Mothers already on HCQ will remain on 400mg, or escalate to 400mg if on 200mg. The primary investigator, [name]., holds a U.S. Federal Drug Administration-issued IND (Investigational New Drug) number (112357) for HCQ.

A. Screening visit: Prior to the qualifying visit, the consent form will be reviewed and signed. Laboratory tests will include: CBC, liver-function tests (routine chemistries; albumin will be important to standardize the effect of physiologic hemodilution of pregnancy in gauging changes in autoantibody titers), urinalysis, and a 24 h collection for measurement of creatinine clearance and protein excretion as deemed appropriate. Serologic profiles will include: measurement of ANA, anti-DNA, C3 and C4. Blood will be drawn for baseline anti-Ro/La titer HCQ level, and IFNαactivity. Only the former will be available prior to qualification for enrollment. In total, 35 ml of blood will be drawn at screening.

B. Qualifying Visit: This is done as soon as Ab status is established, which should take several days (ship overnight and assay in [name] laboratory is one day turnaround time; for [name], it is equivalent). A detailed history and physical examination will be performed. The patient will either be given a prescription for HCQ 200mg, 2 tabs hs, and advised to see an ophthalmologist, or told to maintain dose if 400mg. For women who have SLE, data will be collected to calculate the Systemic Lupus Erythematosus Pregnancy Disease Activity Index (SLEPDAI). Rheumatologists will complete assessment forms, which will be reviewed by Drs. [name] and [name] to address any effect of treatment on underlying SLE activity per se. Of note, [name] has provided these forms for use in the ongoing NIH-supported PROMISSE trial.

C. Follow-up Assessments: Fetal echocardiograms will be performed after enrollment (16-18 weeks) and weekly thereafter until 26 weeks, then biweekly until 34 weeks. Fetal echocardiographic scans will be performed according to standard methods [14,33,39], recorded on VHS videotape or DVD/Optical Disc by the pediatric cardiologist or obstetrician, and sent to the core echocardiographic lab and quantified on data abstraction forms by [name]. After the final fetal echo at 34 weeks, patients will continue with routine obstetric and rheumatologic care as appropriate. Neonates will have an EKG and echocardiogram at birth and at 1-year follow-up (it is acknowledged that this will be

out of the window of LFM award but not affect outcome since to date CHB has not occurred de novo after birth). Each woman will undergo routine obstetrical ultrasounds as per the treating obstetrician. Targeted Level 2 ultrasounds will be required between 21-24 weeks, and between 30-32 weeks to assess fetal well-being. Mothers enrolled in Europe will have their echocardiograms initially read by their primary cardiologists with the tapes then forwarded to [name].

Between 20-25 weeks and 30-35 weeks, and at delivery for all women, 20 ml of blood will be drawn (10 for serum, 10 for plasma and isolation of DNA). Cord blood will also be obtained. Both HCQ levels and IFN-α activity will be evaluated in each sample to serve both as a proxy for compliance and as a potential biomarker of efficacy, respectively. Samples will be sent overnight to [name] lab at each visit (screening, 2nd trimester, 3rd trimester, and delivery), rather than having each site process the bloods, which may be unduly cumbersome for busy obstetrical practices. For patients enrolled in Europe, samples will be stored in [name] lab and shipped in batch. Serum samples will be divided into aliquots of 500 □I: 2 will have sodium azide added (final concentration 0.1%) and be stored at 4oC; remaining samples will be stored without azide at -70oC to form the serum specimen bank available to other investigators with approved research protocols (as in the RRNL). Plasma will be similarly stored. DNA will be stored for future investigations as spawned by the clinical results.

Enrolled patients will continue usual care dictated by their underlying rheumatic disease.

Outcome Measures: The primary outcome is recurrence of advanced heart block: i.e., echocardiogram reveals 2nd or 3rd degree AV block. First-degree block [PR >150 msec, i.e., >(normal mean +3 SD)] [33,39] does not constitute a primary outcome unless it progresses to more advanced block. In these situations the mother will be fully counseled regarding morbidity and mortality of 2nd and 3rd degree block, and discussion regarding data on dexamethasone will be provided. Follow-up will be continued by the patient's treating physician. Secondary outcomes include: 1) Prolonged mechanical PR interval (>150 msec) is detected but does not progress to more advanced AV block. EKG at birth must confirm 1st degree AV block. It is also possible that a fetus developing 1st degree block on study medication might have developed more advanced block in the absence of study medication. The detection of 1st degree block will prompt discussion with the steering committee, treating physician and patient which may lead to treatment with dexamethasone. The mother will be informed of the PRIDE results in which 2 women elected to take dexamethasone and the block reverted to normal sinus rhythm [33]. However, the patient will be informed that we do not know the natural progression or regression of 1st degree block, and that 1st degree block may spontaneously reverse. The mother will continue in the study. 2) Any sign of myocardial injury, without change in cardiac rate or rhythm: a) shortening fraction <28% = 2 SD below normal mean or qualitatively reduced systolic function; b) cardio-thoracic ratio >0.33; c) hydropic changes; d) moderate/severe tricuspid regurgitation. 3) Echocardiographic densities consistent with EFE confirmed postnatally. 4) Fetal death not related to cardiac dysfunction. An autopsy with full evaluation of the heart will be encouraged but cannot be mandated. If AV block or evidence of a cardiomyopathy can be "proven," then these will provide the basis for final categorization. If not possible, the death will not be considered a recurrence rate but will be reported. 5) NL rash. 6) Prematurity (gestational age <37 weeks at birth. 7) Birth weight <10% in the context of gestational age. 8) Abnormal fluid collection.

Evaluation of Ab Levels: This will be done exactly as described for the IVIG trial, using recombinant proteins Ro60, Ro52, and La48 in an ELISA [2].

HCQ levels, This assay will be done in [name] laboratory in France. At each patient encounter, the interval between the last ingestion of HCQ and blood sampling is recorded. HCQ is assayed by HPLC with fluorometric detection as described [35] with minor modifications. The detection limit is 10ng/ml, and the between-day and within-day coefficients of variation are <8%.

IFNα activity: This assay will be done in [name] laboratory and will utilize the WISH cell assay, as we have previously reported in anti-Ro positive mothers of children with neonatal lupus [40].

The reporter WISH cells are incubated with 50% patient plasma or serum for 6 hours. Total mRNA is purified from WISH cell lysates and cDNA synthesized from total mRNAs. Forward and reverse primers are used for the genes MX1, PKR, and IFIT1, which are highly and specifically induced by type I IFN. The relative expression of each of the 3 tested IFN-induced genes is calculated as a fold increase compared to its expression in WISH cells cultured with media alone. The ability of patient serum to cause IFN-induced gene expression in the reporter cells is then compared to the mean and SD induced by healthy donor serum. The number of SD above the mean of healthy donors for each gene is calculated. Data are expressed quantitatively as the sum of the number of SD of each of the three genes above the mean of healthy donors. The 3 transcripts chosen for measurement represent coordinate activation of the IFN- α pathway as would be expected after ligation of the type I IFN receptor, instead of measurement of only one IFN- α -induced transcript which may not accurately represent pathway activation. Patients are considered to have high type I IFN activity if either of the two following criteria are met: 1) 2/3 tested IFN-induced genes are expressed >1 SD above the mean of healthy donors, and at least 1 is greater than or equal to 2 SD above the mean of healthy donors, or 2) 1 IFN-induced gene is expressed greater than 4 SD above the mean of healthy donor sera. If neither criterion is met, the sample is considered to have low type I IFN activity. Two-sided Fisher's exact test (sum of small p's method for observed \geq expected) is used to analyze the categorical data, and Mann-Whitney non-parametric t-test is used to compare quantitative data. All evaluations will be done in batch (with the exception of screening anti-Ro/La) when the patient has completed the study.

Characteristics of the Research Population

Number of Subjects and Subject Recruitment

Stage 1, 19 subjects will be given HCQ. If fewer than 3 recurrences are observed, an additional 51 subjects will be treated in Stage 2 (Years 2-3, seeking a renewal and/or NIH funding). However, if 3 or more recurrences are observed after Stage 1, it will be concluded that HCQ is not effective in preventing CHB. Ultimately, HCQ will be considered efficacious for CHB if fewer than 6 CHB cases occur among 70 subjects evaluated on no potentially confounding medications.

While some subjects will be prescribed the study drug (HCQ) by the PI, [name], or a designated study team member (covered by Consent Form Version 1), many patients will be referred to the study from other sites. In these cases, patients' own doctors will take responsibility for prescribing the study drug, and patients will consent to have their bloods and medical records sent to the investigators at NYU for data and sample analysis (as delineated in Consent Form Version 2). [name] or another study team member will discuss the study with each potential subject and complete the informed consent process prior to enrollment. All subjects (74 in total) will be considered enrolled at NYU and consented using NYU IRB-approved consent forms.

Gender of Subjects

Because the aim of this study is to determine whether hydroxychloroquine use during pregnancy prevents congenital heart block, only female subjects will be recruited.

Age of Subjects

18-45

Racial and Ethnic Origin

No subject will be excluded from participation in this study on the basis of race or ethnic origin.

Eligibility (Inclusion) Criteria

1) Mothers must have anti-Ro and/or anti-La Ab documented in the NYU immunology laboratory (CLIA-approved), which utilizes an ELISA (Immunovision) as well as reactivity on ELISA to at least one of three recombinant antigens (48La, 52Ro, 60Ro, JB laboratory). [name] will likewise

verify Ab in his laboratory. 2) Mothers must have a previous child with cardiac NL, defined herein as: the presence of heart block (1st, 2nd, or 3rd degree) documented by electrocardiogram (EKG), echocardiogram, pacemaker, or statement in the medical record, and/or; presence of cardiac injury, which specifically includes autopsy evidence of a mononuclear infiltrate in the endocardium, myocardium, and pericardium and/or EFE on echocardiogram always associated with cardiac dysfunction. In PITCH, we included women with a prior child with rash; however, recent data generated from the RRNL suggest that recurrence of CHB following rash is 11%, not 18% [34]. Thus, inclusion of previous rash could lead to a falsely lowered recurrence rate, and will therefore be excluded. 3) Intrauterine pregnancy \leq 12 weeks. 4) Mother may be taking \leq 20 mg prednisone because, in our experience, CHB has developed in the presence of this dose. 5) Mother may be asymptomatic, or have a rheumatic disease such as SLE or SS. Maternal health status has not been considered an influence on the development of CHB [1]. 6) Mother may or may not already be taking HCQ. This latter point was discussed with [name], who has published extensively on measurement of HCQ [35,36]. While it might be optimal for the mothers anticipating enrollment in the study to all have been on HCQ prior to conception, this is impractical. Some may never achieve pregnancy and not want to take HCQ unless they conceive (especially those asymptomatic). On the other hand, women with SLE are likely to already be on HCQ and it would limit enrollment to exclude these patients if all must initiate HCQ only at enrollment in the first trimester. Although the accepted dogma is that HCQ requires several months for maximal efficacy in treating rheumatic disease, it is unknown whether this would apply to transplacental passage or fetal levels (which are impossible to measure). [name] suggests that HCQ is probably a three compartment model which includes the circulation, tissues and cells. In the circulation, the half life is approximately 7 days and in the tissues, it is 40 days [37,38]. In [name] experience, steady state blood levels of HCQ are achieved in 4-6 weeks. Thus, dosing the mother no later than 10 weeks gestation should provide sufficient fetal exposure before the vulnerable period of CHB which is generally accepted to span 18-24 wks. Furthermore, the placenta has to be formed for HCQ to gain access to the fetus and it may be effective quickly for the biology we are considering.

Exclusion Criteria

1) Mother does not have Ab to Ro or La. 2) Identification of any of the following structural lesions considered causal for CHB, i.e., those that could account for block because of fibrous disruption between the atrium and AV node or due to absence of the penetrating bundles of the AV node: a) atrioventricular septal defects; b) single ventricle c) developmental tricuspid valve disease; d) L-transposition of the great arteries; e) heterotaxia. 3) Mother is taking >20 mg prednisone/day. Although unlikely to be preventative, higher doses will constitute an exclusion. The final point of intense discussion centered around whether another exclusion should be the use of HCQ in the first pregnancy in which CHB occurred. While one could argue that in these mothers HCQ was not effective and perhaps will not be again, this assumption remains speculative and thus prior absence of efficacy of HCQ will not constitute an exclusion criteria.

Vulnerable Subjects

This study will examine two groups of vulnerable subjects – pregnant women and their fetuses. Congenital heart block associated with maternal anti-Ro antibodies, the rare disease this study seeks to understand and ultimately prevent, affects the fetuses of mother who carry these anti-Ro antibodies. It is therefore essential to include these vulnerable populations in this study, as our ultimate goal is to protect these mothers and their children by understanding and ultimately preventing this devastating disease.

Methods and Procedures
Methods and Procedures

With over 400 families now enrolled in the RRNL and our success at rapid enrollment in PITCH, we are well positioned to enroll in the current study. Most of the women enrolled in the RRNL are of childbearing age, motivation is quite high, and based on review of overall data, it is likely that at least 20% will again become pregnant and available for this study. Importantly, PRIDE and PITCH solidified a referral base of obstetricians and pediatric cardiologists. Furthermore, [name] has agreed to participate given that all 19 patients must be recruited in one year. The DSMB for the U.S. based PITCH study ([name], maternal-fetal medicine, [name], rheumatologist with expertise in pregnancy and women's health issues, and [name], rheumatologist with expertise in design and monitoring of clinical trials in SLE) in conjunction with Drs. [name], [name], [name] (pediatric cardiologist), and [name] (statistician) have had extensive discussions regarding the results of PITCH and the design of this current study. With regard to a randomized trial comparing any drug with placebo, [name] prepared the following analysis:

Assumptions 1. Recurrence rate of CHB (whether previous child had CHB or rash) is approx 19%.

2. Clinically meaningful outcome would be at least 50% reduction in recurrence rate.

Power Calculations 19% to 10% recurrence rate: 261 per group (N = 522)

19% to 5% recurrence rate: 97 per group (N = 194)

Data Analysis And Data Monitoring

Statistical considerations for overall study:

The proposed design has the following operating characteristics. Let p1 = recurrence rate definitely not worthy of further investigation; p2 = recurrence definitely worthy of further investigation. In this study, we define p1 = 18% [41] and p2 = 5%. According to Simon's optimal 2stage approach [32], the expected sample size is 29.8 subjects with a probability of early termination of 0.69 when the recurrence rate is equal to p1. The probability of accepting the treatment for further study is at most 5% if the recurrence rate is unacceptably high (>18%) with that treatment. In contrast, there is a 90% probability of accepting the treatment for further study if the true recurrence rate is 5%. It is important to emphasize that the purpose is to obtain critical data on the efficacy of HCQ in the prevention of recurrent CHB and determine whether this preventive approach should be studied further. At study completion, the proportion of mothers having a child with advanced CHB will also be computed, along with corresponding 95% confidence intervals. Secondary endpoints that are binary (i.e., occurrence of 1st degree block, abnormal fluid collection) will be analyzed by similar approaches. Continuous variables (e.g., shortening fraction, gestational age) will be summarized by estimating means and standard deviations. The effect of therapy on HCQ levels, IFN-α signatures, and Ab titers will be evaluated by fitting mixed effects linear models to repeated assessments of titers obtained during follow-up. In addition, change in any of these analytes at specific time points from baseline will be analyzed using the paired t-test or Wilcoxon signed rank test, depending on distribution of the data.

Safety committee. An independent DSMB will convene by teleconference three times during the year. The members include Drs. [name], [name], and [name] (all of whom served in PITCH).

Data Storage and Confidentiality

Data management. Study information will be recorded at the patients' obstetrical and rheumatology sites. Standardized, computer-adapted case report forms (CRFs) have been developed. Within 2 weeks of each visit, completed CRFs and tapes of the echocardiograms will be sent to [name]. Following review, CRFs will be faxed to the coordinator at NYU for final error checks and entered into the computer database. The coordinator will maintain a calendar for each patient, monitor completion

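### Albumin is named as the correction for pregnancy hemodilution but specified only at screening, and the titre analysis has no dilution term, so a fall from dilution could be misread as an HCQ effect

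*Combined protocol and SAP*

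**What the plan says.** **Screening (Study Design, A. Screening visit).** Routine chemistries are taken, with the reason that "albumin will be important to standardize the effect of physiologic hemodilution of pregnancy in gauging changes in autoantibody titers". The same visit supplies the baseline: "Blood will be drawn for baseline anti-Ro/La titer HCQ level, and IFNαactivity". Inclusion criterion 3 puts enrolment at 12 weeks' gestation or earlier.

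**Follow-up (Study Design, C. Follow-up Assessments).** At 20-25 weeks, 30-35 weeks and delivery, "20 ml of blood will be drawn (10 for serum, 10 for plasma and isolation of DNA"). For these samples, "Both HCQ levels and IFN-α activity will be evaluated in each sample". Neither albumin nor a chemistry panel is named. Serum is divided into aliquots and stored; apart from two azide-treated aliquots, "remaining samples will be stored without azide at -70oC to form the serum specimen bank".

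**Assay timing (IFNα activity paragraph).** "All evaluations will be done in batch (with the exception of screening anti-Ro/La"), once the woman has completed the study.

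**Analysis (Data Analysis And Data Monitoring).** The effect of therapy on HCQ levels, IFN-α signatures and antibody titres is to be evaluated by mixed effects linear models on repeated titres. A second analysis is also given: "change in any of these analytes at specific time points from baseline will be analyzed using the paired t-test or Wilcoxon signed rank test". No covariate is listed for either analysis.

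**The concern.** The protocol identifies a confounder of titre change (hemodilution) and a remedy (albumin), but carries the remedy no further than the first visit. One albumin value at screening cannot correct a change that happens afterwards. Dilution after a first-trimester baseline would tend to move every woman's titre in the same direction. That is a systematic shift, which a paired test detects more readily as the sample grows. With a single arm, change over gestation and change on HCQ cannot be separated, yet the analysis section labels the change an effect of therapy. At stake is the interpretation of the antibody-titre biomarker results.

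**Working it through.** The documents state no expected titre change, power or significance level for this analysis, so there is no figure of the plan's to reproduce. The check has three steps.

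**1. Schedule against stated purpose**

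| Maternal sample | Titre needed for the planned analysis | Albumin named |
|---|---|---|
| Screening (12 weeks or earlier) | yes, baseline | yes |
| 20-25 weeks | yes | no |
| 30-35 weeks | yes | no |
| Delivery | yes | no |

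Standardizing a change from baseline needs albumin in every row.

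**2. Size of the apparent fall (assumed dilution)**

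If plasma volume is a fraction d above its screening value and the antibody mass is unchanged, the apparent fall is 1 − 1/(1+d).

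- d = 0.10: 1 − 1/1.10 = 9.1%
- d = 0.20: 1 − 1/1.20 = 16.7%
- d = 0.30: 1 − 1/1.30 = 23.1%
- d = 0.50: 1 − 1/1.50 = 33.3%

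If albumin is diluted in the same proportion, the titre-to-albumin ratio becomes [T/(1+d)] / [A/(1+d)] = T/A. The expected change from dilution alone is then zero.

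**3. Chance that dilution alone gives a significant paired test (illustration)**

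Assumptions, none from the documents: no HCQ effect; a titre fall f from dilution; SD of the log-titre change between 0.2 and 0.5; two-sided 0.05. The sample sizes of 19 (Stage 1) and 70 (both stages) are the plan's. The noncentrality is |ln(1 − f)| / SD × √n, referred to a noncentral t with n − 1 degrees of freedom.

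Worked example, f = 0.10 and SD = 0.3, with ln(0.90) = −0.1054:

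- n = 19: 0.1054/0.3 × √19 = 1.53, giving 30.5%
- n = 70: 0.1054/0.3 × √70 = 2.94, giving 82.6%

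Ranges below run from SD 0.5 to SD 0.2:

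| Fall from dilution alone | 19 women | 70 women |
|---|---|---|
| 5% | 7-19% | 14-56% |
| 10% | 14-58% | 41-99% |
| 20% | 45% to over 99% | 96% to over 99% |

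A 10% fall corresponds to plasma volume about 11% above screening (1/0.90 = 1.11). The spread shows how far the result depends on two unknowns, the dilution and the variability of titre change. With proportional albumin and the ratio as the analysed quantity, the false-positive rate returns to about 5%.

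**The case against.** Several points on the other side are sound and limit the claim.

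- **The follow-up text is not a full assay list.** It does not name antibody titres either, although the analysis section plainly expects them. A laboratory-data case report form exists, with contents by visit not stated. What can be said is that serial albumin is not specified, not that it will go unmeasured.
- **A reader might infer that the standardization is impossible.** The documents do not support that. Serum from each visit is stored and assays are run in batch, so albumin can still be obtained. What is missing is a commitment to do so and a rule for using it.
- **A reader might infer that the models are unadjusted.** The analysis section is silent on covariates; it does not exclude them.
- **The antibody method is taken from the IVIG trial** (Outcome Measures, Evaluation of Ab Levels). Whether that method handles dilution cannot be seen here. The sentence describes the ELISA and its antigens, and it adds no albumin time point to this trial.
- **The IVIG trial found no significant change in maternal titres**, with 20 mothers completing treatment. This is the strongest evidence against a large shift, and it means that a false finding is not a foregone conclusion. It does not exclude a moderate one. In the illustration, a 10% fall is missed in 42% to 86% of trials of 19 women (100% minus 58% and 14%). That trial also used a different agent.
- **The link to mechanism is indirect.** The HCQ mechanism proposed in the background is reduced transplacental transport of antibody. Maternal titre does not measure that directly, so a spurious fall would not in itself be evidence for it.

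None of these points puts serial albumin or an adjustment into the plan.

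**Conclusion.** The point holds in a limited form. The plan calls albumin important for judging titre change, names it only at screening, and gives no albumin or dilution term in the analysis of titres. With one arm and a baseline at or before 12 weeks, a fall due to dilution could be misread as an effect of HCQ.

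A reader might go further and conclude that such a fall will be attributed to HCQ, or that the trial's conclusion is at risk. The documents support neither. The first depends on a dilution and a variability that they do not give. As to the second, the primary outcome, the stopping rule and the efficacy rule count only second- or third-degree block, and titres are not among the eight listed secondary outcomes.

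The apparent falls of 9% to 33% rest on assumed plasma volumes 10% to 50% above screening with antibody mass unchanged. The false-positive chances rest on assumed SDs as well. The 70-woman figures apply only if Stage 2 opens. The change is worth making because it is cheap and completes what the protocol itself calls important.

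**What to change.** 1. **Follow-up Assessments:** name albumin as an assay on the maternal serum already drawn at 20-25 weeks, 30-35 weeks and delivery, fresh or banked. If banked, reserve an aliquot, since the bank is also open to other investigators.
2. **Data Analysis And Data Monitoring:** analyse titre change as the titre-to-albumin ratio, or with albumin as a time-varying covariate in the mixed model. Choose one in advance and report raw titres beside it.
3. **Same section:** describe the result as change over pregnancy on HCQ rather than as an effect of therapy. Albumin adjustment removes dilution but does not supply a control group.

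**Cost:** 70 women × 3 samples = 210 routine assays and one model term, with no added draw or visit and no change in sample size.

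**Downside:** albumin can fall for reasons other than dilution, for example proteinuria in women with SLE, who are eligible. In such women the ratio would overcorrect and could hide a real fall in titre. This is why raw titres should be shown as well.
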